## 4. ENDPOINTS

### 4.1. Primary Endpoint

The primary endpoint is time-weighted average daily change from baseline in viral load ( $\log_{10}$  copies/mL) from day 1 to day 7, as measured by RT-qPCR in nasopharyngeal (NP) swab samples, in patients who have a central-lab determined RT-qPCR positive test and are seronegative at baseline.

### 4.2. Secondary Endpoints

The secondary endpoints are:

- Time-weighted average daily change from baseline in viral load ( $\log_{10}$  copies/mL) from day 1 to day 5
- Time-weighted average daily change from baseline in viral load ( $\log_{10}$  copies/mL) in patients with high viral load at baseline ( $>10^4$  copies/mL,  $>10^5$  copies/mL,  $>10^6$  copies/mL,  $>10^7$  copies/mL) from day 1 to day 7
- Time-weighted average daily change from baseline in viral load ( $\log_{10}$  copies/mL) in patients with high viral load at baseline ( $>10^4$  copies/mL,  $>10^5$  copies/mL,  $>10^6$  copies/mL,  $>10^7$  copies/mL) from day 1 to day 5
- Proportion of patients with high viral load ( $>10^4$  copies/mL,  $>10^5$  copies/mL,  $>10^6$  copies/mL,  $>10^7$  copies/mL) at each visit
- Proportion of patients with viral loads below the limit of detection at each visit
- Proportion of patients with viral loads below the lower limit of quantification at each visit
- Change from baseline in viral load ( $\log_{10}$  copies/mL) at each visit, as measured by RT-qPCR in NP samples
- Proportion of patients with treatment-emergent SAEs through day 29
- Proportion of patients with infusion-related reactions (grade  $\geq 2$ ) through day 4
- Proportion of patients with injection-site reactions (grade  $\geq 3$ ) through day 4
- Proportion of patients with hypersensitivity reactions (grade  $\geq 2$ ) through day 29
- Concentrations of REGN10933 and REGN10987 in serum over time
- Immunogenicity as measured by ADAs and NAb to REGN10933 and REGN10987

### 4.3. Exploratory Endpoints

*Note: The definition of a COVID-19-related medically-attended visit is provided in Section 9.2.10.3.*

The exploratory endpoints are:

- Time-weighted average daily change from baseline in cycle threshold (Ct) from day 1 to day 7, as measured by RT-qPCR in NP samples
- Time-weighted average daily change from baseline in Ct from day 1 to day 5, as measured by RT-qPCR in NP samples
- Change from baseline in Ct at each visit, as measured by RT-qPCR in NP samples
- Proportion of patients (through day 29 and day 169) with  $\geq 1$  COVID-19-related hospitalization or all-cause mortality
- Proportion of patients (through day 29 and day 169) with  $\geq 1$  COVID-19-related hospitalization, emergency room (ER) visit, or all-cause mortality
- Proportion of patients (through day 29 and day 169) with  $\geq 1$  COVID-19-related medically-attended visit or all-cause mortality
- Proportion of patients (through day 29 and day 169) with  $\geq 1$  COVID-19-related medically-attended visit by type of visit (hospitalization, emergency room visit, urgent care, physician's office visit, and/or telemedicine visit)
- Proportion of patients (through day 29 and day 169) with  $\geq 2$  COVID-19-related medically-attended visits or all-cause mortality
- Days of hospitalization due to COVID-19
- Proportion of patients (by day 29 and day 169) admitted to an intensive care unit (ICU) due to COVID-19
- Proportion of patients (by day 29 and day 169) requiring supplemental oxygen due to COVID-19
- Proportion of patients (by day 29 and day 169) requiring mechanical ventilation due to COVID-19
- Total number of COVID-19-related MAVs through day 29 and 169
- All-cause mortality by day 29 and day 169
- Proportion of patients with treatment-emergent SAEs through day 169

## 5. STUDY VARIABLES

### 5.1. Demographic and Baseline Characteristics

Baseline characteristics will include standard demography (eg, age, race, weight, height), disease characteristics (eg, baseline viral load [ $\log_{10}$  copies/mL, viral load threshold, and Ct], presence/absence of COVID-19-related symptoms, days since symptom onset), serology (negative, positive, or other), medical history, and medication history for each patient.

### 5.2. Efficacy Variables

Efficacy variables include viral load ( $\log_{10}$  copies/mL and Ct).

### 5.3. Safety Variables

Safety variables include incidence of TEAEs, incidence of treatment-emergent SAEs, and incidence of treatment-emergent AESIs as described in Section 10.1.1.

### 5.4. Pharmacokinetic Variables

The variables are the concentration of REGN10933 and REGN10987 in serum and time. Samples will be collected at the visits specified in Table 1.

### 5.5. Immunogenicity Variables

The immunogenicity variables are ADA status, titer, as well as NAb status, and time point/visit. Samples will be collected at the visits specified in Table 1.

## 6. STUDY DESIGN

### 6.1. Study Description and Duration

*Note: as of protocol amendment 2, study enrollment is closed.*

This is a randomized, double-blind, placebo-controlled, parallel group study to assess the dose response profile of single IV or single SC doses of REGN10933+REGN10987 in outpatients with SARS-CoV-2 infection. The schedule of events is provided in Table 1, and the study design is provided in Figure 1.

Eligible patients will be randomized to receive a single dose of REGN10933+REGN10987 or placebo by IV or SC route (refer to Section 8.6 for more information on treatment allocation). On the day of dosing, patients will have NP swabs taken for SARS-CoV-2 RT-qPCR testing and blood drawn for safety, drug concentration, immunogenicity, and serologic analyses. After study drug administration, patients will have a post-dose blood collection (either at the end of intravenous infusion or at least 1 hour after subcutaneous administration). Patients will be monitored for at least 1 hour after study drug administration and then released from the study site, if medically appropriate.

[figure not shown]
Subsequent assessments and sample collections may potentially occur through a variety of in-person and remote methods. This may include (but is not limited to) visits at the study site or place of infusion, home-based visits (defined as visits by home health staff, at mobile units, and/or testing centers), or by phone/telemedicine. Throughout the study, biological samples will be obtained by study personnel only at study locations where appropriate personal protective equipment (PPE) can be used.

Information related to safety and COVID-19-related medically-attended visits will be recorded during planned study visits. Patients will also be asked to notify study personnel as soon as possible about any medically-attended visits. Note that the TEAEs (as defined in Section 10.1.1) that will be collected during the study will differ according to different periods of the study schedule (Table 1). Refer to Section 10.1.1 for more information on reporting of TEAEs and treatment-emergent laboratory abnormalities.

Patients will have NP swabs and blood samples collected every other day for the first week of the study. Additional NP swab samples will be collected once-weekly for 2 more weeks to assess potential persistence of viral load. A phone visit will occur during the fourth week for collection of safety information.

After the first month, patients will have visits approximately once-monthly for 4 additional months. The penultimate visit will be in-person to collect blood samples for drug concentration and immunogenicity. The final visit (EOS) will be a phone call.

**Figure 1: Study Flow Diagram**

## 6.2. End of Study Definition

The end of study is defined as the date when the last living patient completes the last study visit, withdraws from the study, or is lost to follow-up (ie, the study patient can no longer be contacted by the investigator).

## 6.3. Planned Interim Analysis

No formal interim analysis will be conducted. Refer to Section 11.4.9 for information on the timing of planned analyses for this study.

## 7. SELECTION, WITHDRAWAL, AND REPLACEMENT OF PATIENTS

### 7.1. Number of Patients Planned

Up to approximately 1400 patients will be enrolled. Refer to Section 11.2 for more information.

### 7.2. Study Population

This study will enroll adult, non-hospitalized patients who have a positive diagnostic test for SARS-CoV-2.

#### 7.2.1. Inclusion Criteria

A patient must meet the following criteria to be eligible for inclusion in the study:

1. Is male or female  $\geq 18$  years of age (or country's legal age of adulthood) at randomization

*Note: upper age limit may apply; refer to other inclusion criteria.*

2. Has SARS-CoV-2-positive diagnostic test from a sample collected  $\leq 72$  hours prior to randomization, using a validated SARS-CoV-2 antigen, RT-PCR, or other molecular diagnostic assay and an appropriate sample such as nasopharyngeal (NP), nasal, oropharyngeal (OP), or saliva

*Note: Historical record of positive result is acceptable, as long as the sample was collected  $\leq 72$  hours prior to randomization.*

3. *Low-risk symptomatic patient:* Has symptoms consistent with COVID-19 (as determined by the investigator) with onset  $\leq 7$  days before randomization, and **meets all of the following 8 criteria:**

- a. Age  $\leq 50$
- b. No obesity, with obesity defined as BMI  $\geq 30$  kg/m^2
- c. Does not have cardiovascular disease or hypertension
- d. Does not have chronic lung disease or asthma
- e. Does not have type 1 or type 2 diabetes mellitus
- f. Does not have chronic kidney disease, with or without dialysis
- g. Does not have chronic liver disease
- h. Is not pregnant

***or***

*Asymptomatic patient:* Has had no symptoms consistent with COVID-19 (as determined by the investigator) occurring at any time  $< 2$  months prior to randomization

4. Maintains O2 saturation  $\geq 93\%$  on room air
5. Is willing and able to provide informed consent signed by study patient or legally acceptable representative
6. Is willing and able to comply with study procedures, including providing samples for viral shedding testing

### 7.2.2. Exclusion Criteria

A patient who meets any of the following criteria will be excluded from the study:

1. Was admitted to a hospital for COVID-19 prior to randomization, or is hospitalized (inpatient) for any reason at randomization
2. Has a known positive SARS-CoV-2 serologic test
3. Has a positive SARS-CoV-2 antigen or molecular diagnostic test from a sample collected >72 hours prior to randomization
4. Is immunosuppressed, based on investigator's assessment

*Note: examples include cancer treatment, bone marrow or organ transplantation, immune deficiencies, HIV (if poorly controlled or evidence of AIDS), sickle cell anemia, thalassemia, and prolonged use of immune-weakening medications.*

5. Has participated, or is participating, in a clinical research study evaluating COVID-19 convalescent plasma, mAbs against SARS-CoV-2, or intravenous immunoglobulin (IVIG) within 3 months or within 5 half-lives of the investigational product (whichever is longer) prior to the screening visit
6. Prior, current, or planned future use of any of the following treatments: COVID-19 convalescent plasma, mAbs against SARS-CoV-2 (eg, bamlanivimab), IVIG (any indication), systemic corticosteroids (any indication), or COVID-19 treatments (authorized, approved, or investigational)

*Note: prior use is defined as the past 30 days or within than 5 half-lives of the investigational product (whichever is longer) from screening.*

7. Prior use (prior to randomization), current use (at randomization), or planned use (within time period given per CDC guidance but no sooner than 22 days of study drug administration) of any authorized or approved vaccine for COVID-19

*Note: As of 02 March 2021, CDC guidance recommends deferral of SARS-CoV-2 vaccination for at least 90 days after administration of passive antibody therapy. Refer to Section 8.10.1 for more information.*

8. Has known active infection with influenza or other non-SARS-CoV-2 respiratory pathogen, confirmed by a diagnostic test
9. Has known allergy or hypersensitivity to components of study drug
10. Has been discharged, or is planned to be discharged, to a quarantine center
11. Has participated, is participating, or plans to participate in a clinical research study evaluating any authorized, approved, or investigational vaccine for COVID-19
12. Is a member of the clinical site study team or is an immediate family member of the site study team

### 7.3. Premature Withdrawal from the Study

A patient has the right to withdraw from the study at any time, for any reason, and without repercussion.

The investigator and/or Sponsor have the right to withdraw a patient from the study if it is no longer in the interest of the patient to continue in the study, or if the patient's continuation in the study places the scientific outcome of the study at risk (eg, if a patient does not or cannot follow study procedures). An excessive rate of withdrawals would render the study uninterpretable; therefore, unnecessary withdrawal of patients should be avoided.

Patient who are withdrawn prematurely from the study will be asked to complete an early termination visit and follow up contact, as described in Section 9.1.2.

#### **7.4. Replacement of Patients**

Patient prematurely discontinued from the study will not be replaced.

### **8. STUDY TREATMENTS**

#### **8.1. Investigational and Reference Treatments**

Instructions on dose preparation are provided in the pharmacy manual. See Section 8.6 for dose levels and method of treatment allocation.

- Co-administered REGN10933+REGN10987 combination therapy
- Placebo

In this study, both intravenous infusion and subcutaneous administration will be used. All patients allocated to a subcutaneous regimen will receive 4 injections of study drug on day 1, each containing 2.5 mL of active study drug or placebo.

It is recommended that subcutaneous injection sites should be chosen among the different quadrants of the abdomen (avoiding navel and waist areas) and upper thighs. During the dose administration, each injection must be given in a different anatomical location (1 injection administered in the right lower quadrant of the abdomen, another in the left lower quadrant of the abdomen, etc).

#### **8.2. Background Treatment(s)**

No background treatment will be allowed. Patients may self-administer non-prescribed medications (eg, antipyretics).

#### **8.3. Rescue Treatment(s)**

Patients can receive rescue therapy for COVID-19 per local standard-of-care. Rescue treatment(s) will not be provided as part of the study.

#### **8.4. Dose Modification and Study Treatment Discontinuation Rules**

##### **8.4.1. Dose Modification**

This is a single dose study; dose modification is not allowed.

#### 8.4.2. Study Drug Discontinuation

This is a single dose study; study drug discontinuation is not applicable.

### 8.5. Management of Acute Reactions

#### 8.5.1. Infusion-Related Reactions and Hypersensitivity Reactions

Emergency equipment and medication for the treatment of infusion reactions must be available for immediate use if required for treatment. All grade  $\geq 2$  infusion-related reactions and grade  $\geq 2$  hypersensitivity reactions must be reported as AESIs (see Section 10.2.3). Refer to CTCAE severity scale in Section 10.2.5.

##### 8.5.1.1. Interruption of the Intravenous Infusion

The infusion should be interrupted if any of the following AEs are observed:

- Sustained/severe cough
- Rigors/chills
- Rash, pruritus (itching)
- Urticaria (hives, welts, wheals)
- Diaphoresis (sweating)
- Hypotension
- Dyspnea (shortness of breath)
- Vomiting
- Flushing

The reaction(s) should be treated symptomatically, and the infusion may be restarted at 50% of the original rate.

If investigators feel there is a medical need for treatment or discontinuation of the infusion other than described above, they should use clinical judgment to provide the appropriate response according to typical clinical practice.

##### 8.5.1.2. Termination of the Intravenous Infusion

The infusion should be terminated and **not** restarted if any of the following AEs occur:

- Anaphylaxis\*
- Laryngeal/pharyngeal edema
- Severe bronchospasm
- Chest pain
- Seizure
- Severe hypotension

- Other neurological symptoms (confusion, loss of consciousness, paresthesia, paralysis, etc)
- Any other symptom or sign that, in the opinion of the investigator, warrants termination of the IV infusion

\*Consider anaphylaxis if the following is observed ([Sampson, 2006](#)): acute onset of an illness (minutes to several hours) with involvement of the skin, mucosal tissue, or both (eg, generalized hives, pruritus or flushing, swollen lips-tongue-uvula) **and at least one of the following:**

- Respiratory compromise (eg, dyspnea, wheeze-bronchospasm, stridor, reduced peak expiratory flow, hypoxemia)
- Reduced BP or associated symptoms of end-organ dysfunction (eg, hypotonia [collapse], syncope, incontinence)

### 8.5.2. Injection Reactions

Emergency equipment and medication for the treatment of systemic injection reactions (ie, hypersensitivity) must be available for immediate use.

All grade  $\geq 3$  injection reactions (local or systemic) must be reported as AESIs. Refer to CTCAE severity scale in Section [10.2.5](#).

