### 10.1.3. Events that Require Expedited Reporting to Sponsor

The following events also require reporting to the Sponsor (or designee) within 24 hours of learning of the event:

- **Treatment-emergent SAEs.**
- **Treatment-emergent AESI** (serious and nonserious), defined as:
  - Grade  $\geq 2$  infusion-related reactions
  - Grade  $\geq 3$  injection-site reactions
  - Grade  $\geq 2$  hypersensitivity reactions
  - Any TEAE that led to a hospitalization or emergency room visit, regardless of whether the visit is related to COVID-19
- **Pregnancy:** Although pregnancy is not considered an AE, it is the responsibility of the investigator to report to the Sponsor (or designee), within 24 hours of identification, any pregnancy occurring in a female study patient during the study or existing at the

time of signing the informed consent form. A paper pregnancy report form must be completed for each patient who becomes pregnant or is pregnant at the signing of consent.

Any complication of pregnancy affecting a female study patient and/or fetus and/or newborn that meets the SAE criteria must be reported as an SAE. Outcome for all pregnancies should be reported to the Sponsor, including testing results for SARS-CoV-2 infection in the newborn, if performed.

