### 10.2.4. Infusion-Related Reactions, Injection-Site Reactions, and Hypersensitivity Reactions

Infusion-related reactions are defined as any relevant adverse event that occurs during intravenous infusion or up to day 4.

Injection-site reactions are defined as any relevant adverse event that occurs during subcutaneous injection or up to day 4.

Hypersensitivity reactions are defined as any relevant adverse event that occurs during intravenous infusion or subcutaneous injection or up to study day 29.

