4.6.2. Adverse Events of Special Interest

Adverse events of special interest (AESI) are AEs (serious or non-serious) required to be monitored, documented, and managed in a pre-specified manner as described in the protocol. In this study, AESI are listed below (as provided in the protocol), along with each AESI detailed definition: Treatment-emergent AESI (serious and nonserious) are flagged in the CRFs, defined as:

- Grade ≥ 2 infusion-related reactions up to day 4
- Grade ≥ 3 injection-site reactions up to day 4
- Grade ≥ 2 hypersensitivity reactions up to day 29
- Any treatment-emergent AE (TEAE) that led to a hospitalization or emergency room visit, regardless of whether the visit is related to COVID-19

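### Protocol 8.5.2 states a grade 3 AESI threshold for systemic injection reactions, against grade 2 for hypersensitivity elsewhere, so a site following 8.5.2 alone could leave grade 2 systemic reactions unflagged in the SC arms

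*Protocol*

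**What the plan says.** Protocol 8.5.2 covers reactions to injections. Its first paragraph requires that emergency supplies for "treatment of systemic injection reactions (ie, hypersensitivity) must be available for immediate use". Its second paragraph sets the reporting rule: at grade 3 or above, "injection reactions (local or systemic) must be reported as AESIs". It then refers the reader to the severity scale in 10.2.5 and to nothing else.

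Protocol 8.5.1, headed for infusion-related and hypersensitivity reactions, says that at grade 2 or above "hypersensitivity reactions must be reported as AESIs (see Section 10.2.3". Section 10.2.3 passes the AESI definition on to 10.1.3. That section, introduced by "The following events also require reporting to the Sponsor (or designee) within 24 hours of learning of the event", lists hypersensitivity at grade 2 or above and keeps grade 3 or above for injection-site reactions. Section 10.1.1, the Schedule of Events, its footnote 5 and SAP 4.6.2 use the same pair of thresholds.

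On route, Protocol 10.2.4 leaves no doubt: "Hypersensitivity reactions are defined as any relevant adverse event that occurs during intravenous infusion or subcutaneous injection or up to study day 29".

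The proportion of patients with grade 2 or higher hypersensitivity through day 29 is a secondary endpoint in Protocol 4.2 and SAP 1.2.4. On how AESIs are identified, SAP 4.6.2 says: "Treatment-emergent AESI (serious and nonserious) are flagged in the CRFs".

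**The concern.** Every other statement of the rule keeps grade 3 for reactions at the injection site. Section 8.5.2 extends it to systemic reactions, which its own preceding paragraph identifies with hypersensitivity. For a systemic reaction after an SC dose, two AESI thresholds are then in print. After an IV dose there is one.

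Two things are at stake. The first is prompt reporting: an event that 10.1.3 wants with the sponsor within 24 hours might be entered only as an ordinary adverse event. The second is even ascertainment across routes. Safety and tolerability of SC dosing is a stated aim (Protocol 3.2.1). If flags were set less often after SC dosing, any table built on the flag would show a lower SC rate for a reason unrelated to the drug or the route.

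**Working it through.** The plan gives no figure to reproduce, because this is a comparison of texts. Take one case: a systemic allergic reaction for which oral treatment is indicated, which is grade 2 in Protocol Table 3.

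| Section | After SC dosing | After IV dosing |
|---|---|---|
| Protocol 8.5.2 | Below the stated threshold; no AESI report called for | Does not apply |
| Protocol 8.5.1 | AESI | AESI |
| Protocol 10.1.1 and footnote 5 | AESI, recorded to day 29 | AESI, recorded to day 29 |
| Protocol 10.1.3 | AESI, 24-hour report | AESI, 24-hour report |
| SAP 4.6.2 | AESI, to day 29 | AESI, to day 29 |

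The SC column disagrees with itself and the IV column does not. For IV patients both possible labels, infusion-related reaction and hypersensitivity, carry grade 2.

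Would a site read 8.5.2 alone? It is the only acute-reaction section headed for injections. Section 8.5.1 opens with infusion reactions, and both its subsections concern the IV infusion. Section 8.5.1 leads the reader on to the AESI definition through 10.2.3; 8.5.2 does not. Such a reading is plausible but not certain.

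**Patients under the conflicting text.** From the randomisation table in Protocol 8.6, the SC units are 2 + 2 + 1 = 5 of 14, and 5/14 = 35.7%.
- First 816 patients: 816 × 5/14 = 291.
- Planned ceiling of 1400: 1400 × 5/14 = 500. This is an upper limit, since enrolment closed with Amendment 2.

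**Illustration of sensitivity.** The documents give no hypersensitivity rate, so these inputs are assumptions. Let p be the true rate of grade 2 or higher reactions (0.5% to 2%), g the share of them that are exactly grade 2 (50% to 80%), and m the share of those left unflagged at SC sites (50% to 100%). Then flagged rate = p × (1 − g × m).
- Least loss: 1 − 0.5 × 0.5 = 0.75.
- Greatest loss: 1 − 0.8 × 1.0 = 0.20.
- Active SC patients at the ceiling: 1400 × 4/14 = 400. Expected true cases: 400 × 0.005 = 2 to 400 × 0.02 = 8.
- Expected flagged cases: 2 × 0.20 = 0.4 to 8 × 0.75 = 6.

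Under these assumptions, the flagged SC rate would be 20% to 75% of the true rate. The counts are small, so a few missed flags would alter the reported proportion. If sites follow 10.1.3, m = 0 and nothing is lost.

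**The case against.** The strongest reply is that the documents name the governing definition. Section 10.2.3 points to 10.1.3, which demands the 24-hour report at grade 2 without regard to route. Section 8.5.2 does not say that grade 2 systemic reactions are exempt, and a site can satisfy both sections by reporting at grade 2. The words "treatment of systemic injection reactions (ie, hypersensitivity" also stand in the paragraph on emergency supplies, not in the reporting sentence. All of this stands, and it makes the problem a risk rather than a rule that removes reporting.

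Three stronger readings are tempting and are not supported.

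- **That the plan drops 24-hour reporting for these events.** It does not; 10.1.3 requires it.
- **That the secondary endpoint is biased and SC is made to look better tolerated.** The flag in SAP 4.6.2 is itself defined at grade 2 for hypersensitivity, with no split by route. SAP 5.8.1 lists the hypersensitivity table apart from the AESI summaries and does not say that it is built from the flag. All treatment-emergent events are recorded to day 29 (Protocol 10.1.1) and graded (10.2.5), so the data exist for both routes. Bias would need sites to overlook 10.1.3 and also an analysis that relies on the flag alone.
- **That 291 or 500 patients are affected.** Those are patients allocated to SC. The number affected is the number with a grade 2 systemic reaction that a site did not flag, which is unknown and probably small.

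In addition, SC and IV placebo are summarised separately for safety (Protocol 11.3.2, SAP 3.3). Active and placebo SC patients fall under the same text, so the exposure is mainly in the absolute SC rate and in comparisons of IV with SC.

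What remains is an operative reporting sentence that conflicts with the definition for one route only, and a SAP that does not name the data source for the endpoint.

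**Conclusion.** The inconsistency is in the current text and is confined to SC patients, 5 of 14 randomisation units. Its possible effects are a missing AESI flag, a missed 24-hour report and incomplete AESI tables for grade 2 systemic reactions after SC dosing. None of these is shown to have happened. The events themselves are not lost.

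The secondary endpoint is exposed only if it is derived from the CRF flag, which the SAP neither states nor rules out. The 20% to 75% range rests wholly on assumed inputs and shows only that the endpoint would be sensitive to a few missed flags. It is not an estimate.

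The text should be corrected because the change is small and bears on safety reporting and on even ascertainment across routes. No view is taken here on which grade should trigger an AESI report.

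**What to change.** 1. **Protocol.** Reconcile 8.5.2 with 8.5.1, 10.1.1, 10.1.3 and 10.2.4, so that a single AESI threshold for systemic reactions applies to both routes. The choice of threshold is the sponsor's. Add to 8.5.2 a cross-reference to the AESI definition, as 8.5.1 has, and tell the sites.
2. **SAP.** State in 5.8.1 that the hypersensitivity endpoint, already fixed at grade 2 or higher through day 29, is derived in both routes from all graded treatment-emergent events of that type and not from the AESI flag alone. Name the terms that count.
3. **Data already collected.** Enrolment is closed, so rewording does little for reactions that have already occurred. Re-check recorded grade 2 treatment-emergent events in SC patients for systemic reactions that were not flagged, using staff blinded to active versus placebo.

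The cost is a sentence in each document, a site memo and a small amount of extra data review. No new data are needed, since these events are already recorded and graded.
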